4.3 Inclusion Criteria

It is recommended that patients should have a WOMAC A pain sub score of < 1.5 as measured by the 5-point Likert Pain Subscale in the contralateral knee, which is assessed at screening. Patients should fulfill the following inclusion criteria:

1. Able to provide written informed consent to participate in the study
2. Willing and able to comply with all study requirements and instructions of the site study staff
3. Male or female, 40 years to 85 years old (inclusive)
4. Must be ambulatory
5. Index knee must be symptomatic for greater than six months with a clinical diagnosis of OAK and supported by radiological evidence (Kellgren-Lawrence Grade 4) that is not older than six months prior to the date of screening
6. Moderate to moderately-severe OA pain in the index knee (rating of at least 1.5 on the WOMAC Index 3.1 as measured by the 5-point Likert Pain Subscale,) assessed at screening
7. Ability to temporarily discontinue NSAID for 48 hours prior to scheduled clinical efficacy evaluations
8. No analgesia (including acetaminophen [paracetamol]) taken 12 hours prior to an efficacy measure
9. No known clinically significant liver abnormality (e.g. cirrhosis, transplant, etc.)

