6.1.1 WOMAC® Osteoarthritis Index ([Bellamy 1988](#))

The clinical effects of treatment on OA pain and function will be evaluated during clinic visits at 6, 12, and 24 weeks, and telephone contacts at 2, 4, 8 and 10 weeks, using the WOMAC Index

3.1, and the PGA. All patients are required to take at least five minutes to complete the questionnaire.

Patients are asked about their pain, stiffness, and function in the knee (study joint) due to arthritis during the last 24 hours.

In addition to WOMAC scoring during clinic visits, daily WOMAC A pain sub scores will be collected for seven days up to and including Baseline and Week 12 to allow for calculation of WOMAC A weekly pain scores, which will be used for conducting the primary efficacy analysis.

Patients respond to each subscale by using a 5-point adjectival Likert score (0 = None, 1 = Mild, 2 = Moderate, 3 = Severe, 4 = Extreme) and 100mm VAS.

The WOMAC B and WOMAC C sub scores will be collected at Weeks 0 (Baseline), 2, 4, 6, 8, 10, 12, and 24 using the 5-point Likert scale. Patients respond to each subscale by using a 5-point adjectival Likert score (0 = None, 1 = Mild, 2 = Moderate, 3 = Severe, 4 = Extreme).

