10.4 STUDY ENDPOINTS

10.4.1 Co-Primary Endpoints

- 1) Change in the WOMAC Osteoarthritis Index 3.1 pain sub score as measured by the 5-point Likert scale between Baseline and Week 12.

The primary variable is the average score of the five WOMAC A (pain) subscale questions:

In the last 12 hours, how much pain have you had in the study knee:

1. When walking on a flat surface?
2. When going up or down stairs?
3. At night while in bed? (that is - pain that disturbs your sleep)
4. While sitting or lying down?
5. While standing?

The primary analysis will include the repeated measures of WOMAC A pain sub score from Baseline to Weeks 2, 4, 6, 8, 10, and 12 and will use a mixed-effects model with repeated measures MMRM model, with Treatment assignment, Week, and Baseline WOMAC A pain sub score as fixed effects, and including patient ID as a repeated measure with a compound symmetric covariance matrix for residuals.

- 2) Change in the WOMAC Osteoarthritis Index 3.1 function sub score as measured by the 5-point Likert scale between Baseline and Week 12.

The primary variable is the average score of the seventeen WOMAC C (function) subscale questions.

The primary analysis will include the repeated measures of WOMAC C function sub score from Baseline to Weeks 2, 4, 6, 8, 10, and 12 and will use a mixed-effects model with repeated measures, with Week as a fixed effect, and including patient ID as a repeated measure with a compound symmetric covariance matrix for residuals.

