### **2.4 Sample Size**

This trial will use an adaptive design with promising zone method for sample size re-estimation.

This trial is designed for 1,034 patients, 517 per study arm, randomized 1:1 for Ampion and saline IA injection. There will be an interim analysis when at 724 patients, 362 per study arm, have completed their Week 12 visit.

A promising zone analysis will be performed at the interim. Following the interim analysis, enrollment will either a) continue up to a total of 1034 patients, 517 patients per study arm, randomized 1:1 for Ampion and saline IA injection; b) allow for sample size re-estimation up to a maximum of 1.5 times the original trial size for a total of 1,552 patients, 776 per study arm, randomized 1:1 for Ampion and saline IA injection.

The Ampion effect was estimated as the average change in pain from Baseline to Week 12 for KL 4 subjects receiving Ampion from all prior single injection studies randomized 1:1 with saline control. Saline effect was estimated as the average change in pain from Baseline to Week 12 for KL 4 subjects receiving saline from all prior single injection studies randomized 1:1 for Ampion and saline. The sample size for assessing the WOMAC A Pain score alone would be 690 total patients for 90% power.

The Ampion effect was estimated as the average change in function from Baseline to Week 12 for KL 4 subjects receiving Ampion from all prior single injection studies randomized 1:1 with saline control. Saline effect was estimated as the average change in function from Baseline to Week 12 for KL 4 subjects receiving saline from all prior single injection

studies randomized 1:1 for Ampion and saline. The sample size for assessing the WOMAC C Function score alone would be 984 patients for 90% power.

The total sample size is chosen as the larger of the two values. To be conservative sample sizes were estimated with a 5% dropout so 1,034 patients will be enrolled to achieve 984 total patients. All ITT patients will be included in the statistical analysis. At the assumed effect size there is a 90% probability of success at 1,034 patients.

The study design of 1,034 total patients achieves 97% power assuming a WOMAC A pain score with mean pain decreases of -0.83 for Ampion and -0.62 for saline and a standard deviation of 0.85.

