### 8.6.5 Exploratory Endpoints

A Bayesian meta-analysis for Likert WOMAC A pain subscore including KL4 patients from studies AP-003-A, AP-003-B, AP-003-C, AP-004, and AP-013. The model is constructed for WOMAC A change from baseline for patient  $i$  in study  $j$

$$Y_{i,j} \sim N(\mu_{i,j}, \sigma^2)$$

$$\mu_{i,j} = \alpha_j + \delta_j T_i + \beta BL_i$$

$$\alpha_j \sim N(\alpha, \sigma_\alpha^2)$$

$$\delta_j \sim N(\delta, \sigma_\delta^2)$$

$$\alpha \sim N(0, 100)$$

$$\delta \sim N(0, 100)$$

$$\sigma_\alpha \sim U(0, 10)$$

$$\sigma_\delta \sim U(0, 10)$$

$$\sigma \sim U(0, 10)$$

Where  $T_i$  is the treatment assignment (0 saline or control; 1=Ampion) and  $BL_i$  is the baseline WOMAC A score.  $\alpha_j$ 's represent the control means across studies.  $\delta_j$ 's represent the treatment effects across studies.  $\sigma_\alpha$  and  $\sigma_\delta$  represent the heterogeneity of control rates and treatment effects, respectively. Sensitivity analyses will be reported that increase the priors on the variance parameters from  $U(0, 10)$  to  $U(0, 500)$ . The posterior means and 95% credible intervals will be reported for each treatment by study and treatment effect by study.

Change in WOMAC A pain sub score between Baseline and Weeks 2, 4, 6, 8, 10, and 24 will be analyzed using the MMRM model described for the primary analysis.

Change in WOMAC B stiffness sub score between Baseline and Weeks 2, 4, 6, 8, 10, 12 and 24 will be analyzed using the MMRM model described for the primary analysis.

Change in WOMAC C physical function sub score between Baseline and Weeks 2, 4, 6, 8, 10, and 24 will be analyzed using the MMRM model described for the primary analysis.

Change in PGA between Baseline and Weeks 2, 4, 6, 8, 10, and 24 will be analyzed using the MMRM model described for the primary analysis.

OMERACT-OARSI responder status, defined using Scenario D criteria, will be analyzed using separate logistic regression models for each visit.

Treatment failures will be analyzed with a Fisher's exact test.

Cumulative distribution function (CDF) plots will be used to compare WOMAC A pain and WOMAC C function endpoints for Ampion vs. saline arms.

If collected, the differences in urine analysis will be evaluated between treatment groups at Week 12.

Continuous secondary endpoints and their change from Baseline will be summarized by visit and treatment arm. Change from Baseline will include a 95% CI.

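### The SAP calls the α_j of the Bayesian meta-analysis control means, but baseline pain enters uncentred and no baseline is named at which arm results by study are reported

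*SAP*

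**What the plan says.** SAP 8.6.5 gives the mean for patient i in study j as "\mu_{i,j} = \alpha_j + \delta_j T_i + \beta BL_i". It states that BL_i "is the baseline WOMAC A score" and mentions no centring. It then says that the α_j "represent the control means across studies", that the δ_j are the treatment effects, and that σ_α and σ_δ describe heterogeneity of the control results and of the treatment effects.

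The planned output is: "The posterior means and 95% credible intervals will be reported for each treatment by study and treatment effect by study". The SAP gives no formula for an arm mean. Protocol 10.4.3 leaves the method of this analysis to the SAP, so nothing elsewhere completes it.

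Three other places bear on the point:
- Protocol 10.4.1: "The primary variable is the average score of the five WOMAC A (pain) subscale questions". With items scored 0 to 4 (Protocol 6.1.1), baseline is also on a 0 to 4 scale.
- Protocol 4.3 requires a "rating of at least 1.5 on the WOMAC Index 3.1" at screening. Protocol 1.5 describes the same floor for the earlier studies.
- SAP 2.4 plans for "mean pain decreases of -0.83 for Ampion and -0.62 for saline", with a standard deviation of 0.85.

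**The concern.** Setting T = 0 and BL = 0 in the model returns α_j. So α_j is the predicted change of a saline patient with no pain at baseline, and no such patient is expected in these studies. It equals a control mean only if β = 0. Because the outcome is a change from baseline, β is the slope of follow-up on baseline minus 1, so it is zero only if that slope is exactly 1.

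The label matters because it reaches a promised output. The SAP attaches a meaning only to α_j (control mean) and δ_j (treatment effect). The natural literal reading of an arm result by study is therefore α_j for saline and α_j + δ_j for Ampion. Reported that way, both would be extrapolations to baseline 0. Their level would be shifted, and their intervals would carry the uncertainty of β multiplied by the distance from 0 to the mean baseline.

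**Working it through.** **Inputs from the documents.** Planned changes are -0.62 (saline) and -0.83 (Ampion), SD 0.85 (SAP 2.4). AP-013 has 517 patients per arm. KL 4 patients in the earlier studies number 75 (AP-003-A), 132 (AP-003-B), 168 (AP-003-C) and 210 (AP-004) (Protocol Table 1.2). The total is 75 + 132 + 168 + 210 + 1,034 = 1,619.

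**Assumptions, not in the documents.** β from -0.2 to -0.6 (higher baseline, larger fall); mean baseline 2.0 to 2.8; baseline SD 0.4 to 0.8; residual SD 0.82. The SAP lists no prior for β; N(0, 100) was used in the fitted check.

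**1. The plan's own figure.** SAP 8.6.5 gives no figure for the meta-analysis, so this step only checks the planning values. A difference of 0.21 with SD 0.85, one-sided 0.025 and 90% power needs 2 × (1.960 + 1.282)² × 0.85² / 0.21² ≈ 344.3, hence 345 per arm and 690 in total, as stated. Power is 97.8% with 517 per arm and 97.2% with 492 per arm, against 97% stated.

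**2. Shift in level.** The saline mean is α_j + β × (mean baseline), so α_j = saline mean - β × (mean baseline). The quantity α_j + δ_j is shifted by the same amount. Each cell shows saline / Ampion as they would be read from the parameters:

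| β | mean baseline 2.0 | 2.4 | 2.8 |
|---|---|---|---|
| -0.2 | -0.22 / -0.43 | -0.14 / -0.35 | -0.06 / -0.27 |
| -0.4 | +0.18 / -0.03 | +0.34 / +0.13 | +0.50 / +0.29 |
| -0.6 | +0.58 / +0.37 | +0.82 / +0.61 | +1.06 / +0.85 |

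The shift runs from 0.2 × 2.0 = 0.40 to 0.6 × 2.8 = 1.68. The saline value turns positive once -β × mean baseline exceeds 0.62. That means β below -0.31 at mean baseline 2.0 (0.62 / 2.0) and below -0.22 at 2.8 (0.62 / 2.8).

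**3. Interval width for the AP-013 saline mean.** At the mean baseline, SE ≈ 0.82/√517 = 0.036. At baseline 0 it is √(0.036² + [mean baseline × SE(β)]²), with SE(β) ≈ 0.82/(baseline SD × √1,619).
- Mean 2.0, SD 0.8: SE(β) = 0.025, SE = 0.062, ratio 1.7.
- Mean 2.4, SD 0.5: SE(β) = 0.041, SE = 0.104, ratio 2.9.
- Mean 2.8, SD 0.4: SE(β) = 0.051, SE = 0.147, ratio 4.1.

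**4. Check by fitting the model.** The SAP model was fitted by Gibbs sampling to simulated data of the five study sizes (mean baseline 2.20, true saline change -0.62), once with raw and once with centred baseline.
- Raw baseline: α_j from -0.32 to -0.21 (β = -0.2), +0.12 to +0.23 (β = -0.4) and +0.57 to +0.67 (β = -0.6).
- Centred baseline: α_j from -0.67 to -0.56 in all three cases. Adding fitted β × 2.20 to the raw α_j gives the same values.
- δ_j: -0.23 to -0.27 either way, agreeing within 0.001.
- Posterior mean of σ_α: 0.091 to 0.095 raw, 0.088 to 0.092 centred. Posterior mean of σ_δ: 0.075 to 0.079 raw, 0.074 to 0.078 centred.
- At β = -0.4 the raw 95% interval for the AP-013 α_j was 0.01 to 0.41, which excludes the true saline change.

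**The case against.** The strongest reply is that the SAP does not commit anyone to reporting the raw parameters. It defines the full mean, including the baseline term, and an analyst could evaluate that at a sensible baseline and obtain correct arm means. Centring only reparameterises the same likelihood, so on this view the fault is one of labelling and reporting. That stands, and it makes the consequence conditional: the arm results are wrong only if taken from the parameters as the SAP labels them. It does not rescue the label, which is false for the model printed beside it, and it leaves the reference baseline unstated.

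A reader might also infer that σ_α would measure scatter of extrapolated intercepts and not of control results. The model does not support that. With one β common to all studies, moving the reference from 0 to an overall mean adds the same constant to every α_j, so their spread is practically unchanged.

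Three further limits stand:
- The documents contain no β, mean baseline or baseline SD, so size and sign rest on assumed ranges.
- Arm means adjusted to a common baseline will also differ from a study's observed mean change where that study's mean baseline differs. A mismatch with observed means is therefore not in itself the defect.
- AP-013 mean changes by arm are reported separately with 95% confidence intervals (SAP 8.6.1), so an implausible arm result there would probably be noticed.

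**Conclusion.** The point holds as an incorrect stated interpretation that reaches a promised output. With baseline uncentred, α_j is the expected saline change at baseline pain 0 and is a control mean only if β = 0. AP-013's analysed baseline is a diary average (Protocol 10.3.6) and could fall somewhat below the screening floor of 1.5, but 0 remains an extrapolation.

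Read as labelled, arm results would be shifted by about +0.4 to +1.7 points, and the interval for the AP-013 saline mean would be roughly 1.7 to 4 times too wide, under the assumed ranges above. A reader might infer that both arms are bound to appear to worsen. That is not supported: at β = -0.2 both arms stay negative across the whole baseline range.

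The importance is low. δ_j, δ, σ_δ and σ_α are practically unchanged. The analysis is exploratory, has no decision rule and lies outside the testing hierarchy (SAP 8.6.7), so the co-primary conclusions are untouched.

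**What to change.** In SAP 8.6.5, replace β·BL_i by β·(BL_i - B), where B is the overall mean baseline WOMAC A of the KL 4 patients in the five studies. Then α_j and α_j + δ_j are the saline and Ampion means in study j adjusted to that common baseline, and should be described so. Equivalently, keep the model and define the reported arm means as α_j + β × B and α_j + δ_j + β × B, naming the reference value B. State the prior for β in the same edit, since the section lists none.

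The cost is one term or one sentence. No new data are needed, and the treatment effects do not change in practice.

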### **8.6.6 Post Hoc/Ad Hoc Analyses**

Any analysis not described in this plan will be considered post-hoc and identified as such in the CSR.

### **8.6.7 Multiplicity Adjustment**

Hierarchical testing for the ITT analysis population will be applied to the analysis of the primary endpoints. It will also be utilized for the secondary endpoints, assuming significance of the co-primary effectiveness endpoints are established. Given significance

for the primary effectiveness tests (WOMAC A and WOMAC C (as specified)), then and only then would PGA score be tested at the one-sided alpha of 0.025; if the PGA score is significant then and only then, will the 100 mm VAS hypotheses be tested at a one-sided alpha of 0.025; if the 100 mm VAS hypothesis is significant then, and only then, will the amount of rescue analgesia through Week 12 be tested at a one-sided alpha 0.025. Multiplicity adjustment will not be applied to exploratory endpoints.

## **9. CHANGES FROM PROTOCOL-SPECIFIED ANALYSES**

Modifications to the planned statistical analyses should be minimized. Nonetheless, the data obtained from the study may indicate that the planned analyses are inappropriate, that additional analyses need to be performed, or that the design of the study needs to be modified, due to factors such as the distribution of the data or imbalance in important covariates. The study report will provide a detailed explanation for any deviations from the planned analyses.

## **10. LIST OF PLANNED TABLES, FIGURES, AND LISTINGS**

Tables are categorized and numbered in accordance with ICH E3 guidelines. Each table, figure and listing is presented by treatment arm.

Accountability tables listed below will also include an overall column. Listings will be sorted by treatment, patient ID, and by visit, if multiple visits exist.

### **10.1 Tables**

#### **14.1 Accountability**

14.1.1	Accountability (Analysis population: All Enrolled)
14.1.2	Enrollment by Site (Analysis population: All Enrolled)
14.1.3	Analysis Populations (Analysis population: All Enrolled)
14.1.4	Patient Disposition (All Screened)
14.1.5	Major Protocol Deviations (Analysis population: All Enrolled)
14.1.6.1	Demographics and Baseline Characteristics (Analysis population: ITT)
14.1.6.2	Demographics and Baseline Characteristics (Analysis population: PP)

The following efficacy tables will be provided both for ITT and PP. ITT tables will have a .1 suffix and PP tables will have a .2 suffix added to the table numbers (ex. 14.2.1.1 = ITT and 14.2.1.2 = PP)

#### **14.2 Efficacy**

14.2.1	Summary of WOMAC A Pain Subscale
14.2.2	Summary of WOMAC B Stiffness Subscale
14.2.3	Summary of WOMAC C Physical Function Subscale
14.2.4	Summary of 100mm VAS Pain Score
14.2.5	Summary of PGA
14.2.6	Summary of Rescue Analgesia Use
14.2.7	Summary of OMERACT-OARSI responder rates
14.2.8	Summary of WOMAC A Pain Subscale by Age

14.2.9	Summary of WOMAC A Pain Subscale by Sex
14.2.10	Summary of WOMAC A Pain Subscale by Race
14.2.11	Summary of WOMAC A Pain Subscale by Ethnicity
14.2.12	Summary of WOMAC C Pain Subscale by Age
14.2.13	Summary of WOMAC C Pain Subscale by Sex
14.2.14	Summary of WOMAC C Pain Subscale by Race
14.2.15	Summary of WOMAC C Pain Subscale by Ethnicity
14.2.16	Summary of 100mm VAS Pain Score by Age
14.2.17	Summary of 100mm VAS Pain Score by Sex
14.2.18	Summary of 100mm VAS Pain Score by Race
14.2.19	Summary of 100mm VAS Pain Score by Ethnicity
14.2.20	Summary of PGA by Age
14.2.21	Summary of PGA by Sex
14.2.22	Summary of PGA by Race
14.2.23	Summary of PGA by Ethnicity
14.2.24	Summary of Rescue Analgesia Use by Age
14.2.25	Summary of Rescue Analgesia Use by Sex
14.2.26	Summary of Rescue Analgesia Use by Race
14.2.27	Summary of Rescue Analgesia Use by Ethnicity
14.2.28	Summary of treatment failure rates (%)

### **14.3 Safety**

14.3.1	Overall Summary of Treatment-Emergent Adverse Events (Analysis population: Safety)
14.3.2	Incidence of Treatment-Emergent Adverse Events by System Organ Class and Preferred Term (Analysis population: Safety)
14.3.3	Incidence of Treatment-Emergent Adverse Events by System Organ Class and Preferred Term by Maximum Severity (Analysis population: Safety)
14.3.4	Incidence of Treatment-Emergent Related Adverse Events by System Organ Class and Preferred Term (Analysis population: Safety)
14.3.5	Incidence of Treatment-Emergent Related Adverse Events by System Organ Class and Preferred Term by Maximum Severity (Analysis population: Safety)
14.3.6	Incidence of Treatment-Emergent Serious Adverse Events by System Organ Class and Preferred Term (Analysis population: Safety)
14.3.7	Incidence of Treatment-Emergent Adverse Events by Preferred Term in Descending Order of Frequency (Analysis population: Safety)
14.3.8	Incidence of Treatment-Emergent Related Adverse Events by Preferred Term in Descending Order of Frequency (Analysis population: Safety)
14.3.9.1	Summary of Vital Signs and Change from Baseline over Time for Pulse (bpm) (Analysis population: Safety)
14.3.9.2	Summary of Vital Signs and Change from Baseline over Time for Temperature (F) (Analysis population: Safety)
14.3.9.3	Summary of Vital Signs and Change from Baseline over Time for Systolic BP (mmHg) (Analysis population: Safety)

14.3.9.4	Summary of Vital Signs and Change from Baseline over Time for Diastolic BP (mmHg) (Analysis population: Safety)
14.3.9.5	Concomitant Medication Use by ATC Level 1 and WHO Preferred Term (Analysis population: Safety)
14.3.9.6	Medication Started on Study by ATC Level 1 and WHO Preferred Term (Analysis population: Safety)
14.3.9.7	Concomitant Medications by WHO Preferred Term in Descending Order of Use (Analysis population: Safety)
14.3.9.8	Medication Started on Study by WHO Preferred Term in Descending Order of Use (Analysis population: Safety)

## **10.2 Listings**

### **Subject Accountability**

1. Randomization List (including: patient ID, randomization number, randomized treatment and treatment administered, and date of treatment)
2. Inclusion and Exclusion Criteria
3. Protocol Deviations
4. Patients Withdrawing from the Study Prematurely (date and reason)
5. Analysis Populations with Reason for Exclusion (if populations differ)

### **Demographics and Baseline Characteristics**

6. Demographics and Baseline Characteristics (age, sex, race, ethnicity, weight, height, Baseline WOMAC and PGA scores)
7. Medical History
8. Baseline Medication Use

### **Efficacy**

9. WOMAC A, B, and C Scores (includes all subscales)
10. PGA Scores
11. 100mm VAS Pain Scores
12. Rescue Analgesia
13. OMERACT-OARSI responder rates
14. Treatment failures

### **Safety**

15. All Adverse Events [with indication of TEAE]
16. Physical Exams

17. Vital Signs Data [systolic and diastolic blood pressure, pulse rate, respiration, and temperature]

### **10.3 Figures**

Note that all figures, unless otherwise stated, will be line plots showing mean  $\pm$  SEM at each visit for each treatment arm.

1. WOMAC A Pain Subscale at Baseline and Week 12 [Boxplot]
2. Summary of WOMAC A Pain Subscale over Time
3. Summary of WOMAC B Stiffness Subscale over Time
4. Summary of WOMAC C Physical Function Subscale over Time
5. Summary of PGA over Time
6. Summary of Rescue Analgesia Used [stacked histogram]
7. Summary of OMERACT-OARSI responder rates over time [Bar chart]
8. Change in WOMAC A Pain Subscale from Baseline to Week 12 for subgroups [Forest plot]
9. Change in WOMAC C Function Subscale from Baseline to Week 12 for subgroups [Forest plot]

